1. INTRODUCTION

1.1 BACKGROUND

Interstitial lung disease (ILD) is a diverse group of entities that cause damage to the lung parenchyma through varying degrees of inflammation and fibrosis. Fibrotic ILDs result in restrictive ventilatory physiology and impaired gas exchange, frequently leading

to exertional hypoxemia and functional limitation (1). These diseases have been classified into various groups: ILD of known cause such as occupational or environmental exposures including Pneumoconiosis and Hypersensitivity Pneumonitis, ILD associated to connective tissue diseases/vasculitis, idiopathic interstitial pneumonias including idiopathic pulmonary fibrosis (IPF) and nonspecific interstitial pneumonia (NSIP), granulomatous ILD such as sarcoidosis and other rare forms of ILD including lymphangiomyomatosis (2, 3, 4). Among all these diseases the most common is IPF whose number of deaths in the UK according to the data from the office of national statistics increased from 1.66 per 100,000 people in 1979 to 8.29 per 100,000 people in 2016 (5). The mechanisms of reduced exercise capacity in ILD are multi-factorial. Impaired gas exchange occurs as a result of destruction of the pulmonary capillary bed and thickening of the alveolar-capillary membrane, resulting in ventilation-perfusion mismatch and oxygen diffusion limitations. Circulatory limitation results from pulmonary capillary destruction and pulmonary vasoconstriction and leads to pulmonary hypertension and cardiac dysfunction in some patients. Ventilatory limitations to exercise may also occur, although these are not thought to be a major contributor in most patients (6, 7). Peripheral muscle dysfunction is also a key factor to exercise limitation. Patients who suffer from ILD tend to avoid activities that trigger dyspnoea and fatigue, consequently they reduce their levels of physical activity, which leads to physical deconditioning and increasing symptoms. Furthermore, treatment with corticosteroids and immunosuppressants, as well as systemic inflammation, may also negatively impact on peripheral muscle function in some patients with ILD (6, 7). Pulmonary rehabilitation is an evidence-based, multidisciplinary and comprehensive intervention for patients with chronic respiratory disease who are symptomatic and often have decreased daily life activities. PR programmes include exercise training - which is the cornerstone of PR and includes aerobic conditioning, strength and endurance training respiratory therapy, education, nutritional interventions, psychological and social support and behaviour modification techniques (8, 9, 10). PR can be performed in different places; such as hospital outpatient departments, community health centres and even at home, showing similar results. PR has demonstrated improvements in symptoms, exercise tolerance and quality of life in chronic respiratory diseases other than COPD, including ILD and pulmonary hypertension, despite differences in underlying pathophysiology among them. Nevertheless, there is much less evidence of these improvements and the mechanisms by which pulmonary rehabilitation might improve outcomes in ILD compared to COPD (6, 7). Despite this, guidelines for pulmonary rehabilitation recommend its use in patients with chronic respiratory disorders other than COPD. Emerging evidence suggests that pulmonary rehabilitation may result in meaningful short-term benefits in patients with ILD, mainly on exercise tolerance, muscle function, dyspnoea and quality of life. However, the magnitude of these benefits is smaller than those generally seen in COPD and its ongoing effects are not evident six months after training (7). This may reflect the challenges in providing pulmonary rehabilitation for conditions such as idiopathic pulmonary fibrosis (IPF) that can be rapidly progressive (11). Guidelines for clinical management ILD point out that more information is needed on the benefits of pulmonary rehabilitation for this group of patients (7, 12). The greater prevalence of exercise-induced hypoxia, pulmonary hypertension and arrhythmia compared with other chronic lung diseases in this patient population raises the possibility that response to exercise rehabilitation may also differ (6, 7). In turn, high flow nasal oxygen allows the delivery of a well humidified high flow of air with a mix of oxygen from 21 to 100% and also provides a low level of positive end-expiratory pressure (PEEP). This strategy can achieve higher values of oxygenation even in acutely ill patients with ILD (13, 14) and may

constitute a strategy to ameliorate hypoxemia triggered by exercise in these patients and therefore increase the tolerance to higher training loads.

1.2 RATIONALE FOR CONDUCTING THIS STUDY

Patients with fibrotic ILD have greater oxygen desaturation during 6MWT compared to patients with COPD when adjusting for demographic features and pulmonary physiology. These findings suggest the need for disease-specific studies to evaluate the potential utility of ambulatory oxygen in fibrotic ILD (1). In general, these diseases manifest as dyspnoea on exertion. Progression of disease results in marked exercise limitation, predominantly due to impairment of gas exchange and secondarily due to pulmonary hypertension and other mechanisms including muscle deconditioning. These patients require high levels of supplemental oxygen (> 6 L/min) to sustain daily activities (15), which could not be satisfied using traditional oxygen delivery methods comfortably. High-Flow Nasal Oxygen might potentially be an alternative to conventional oxygen therapy in patients requiring both high flows and high oxygen concentrations to correct hypoxemia and control dyspnoea, however the evidence is still limited (13, 16,). HFNO can deliver very high flows (up to 60 L/min) and utilizes an air oxygen blend allowing from 21 to 100% FIO₂ delivery (13, 14). Furthermore, this system facilitates the delivery of humidified oxygen and improve gas exchange by delivering a small amount of Positive End Expiratory Pressure (PEEP). In turn, HFNO contributes to reduce PaCO₂ by reducing the death space (i.e. washout of CO₂ from the upper airway) (13, 14). It has been demonstrated that patients with Idiopathic pulmonary fibrosis (IPF) have reduced exercise tolerance, which can be assessed among other tests with a CPET, constant work rate exercise test (CWRET), six minute walking test (6MWT), incremental/endurance shuttle walking test (ISWT/ESWT) among other tests. A lower exercise capacity is related to a worse mortality rate. Exercise training has shown to improve exercise tolerance, functional capacity, dyspnoea and quality of life in patients with IPF. Exercise-induced hypoxaemia is sometimes seen in patients with IPF even without resting hypoxaemia, and has been shown to increase mortality risk. Although the IPF guidelines recommend that IPF patients with resting hypoxaemia receive supplemental long-term oxygen therapy, the clinical benefit of exertional supplemental oxygen is unclear in patients with exertional hypoxaemia without resting hypoxaemia. Possible physiological benefits of oxygen supplementation on exercise in IPF may include alterations of muscle metabolism, improvements in oxygen transport at the periphery and improvements in muscle oxidative capacity (17).

Furthermore, it is important to explore and optimize the relationship between outcomes (i.e. improvement on exercise tolerance and quality of life) and the characteristics of the exercise training programme. It is also important to further explore strategies that, by minimising the oxygen desaturation, can allow patients to exercise at higher loads (7).

Strategies to increase the load of training include:

- **High Intensity Interval Training (HIIT):** This strategy, opposite to constant work rate exercise, divides the training load into bouts of high-intensity exercise divided by resting periods. This reduces desaturation, lowers ventilatory (circa 20%) and heart rate response and, therefore enables longer tolerance to exercise (circa 60%) (12).

- Compared to conventional programmes, high-intensity programmes have shown superior and longer-lasting results in other chronic pulmonary diseases. The limitations of high-intensity exercise tolerance in ILD patients such as desaturations and ventilatory limitations can be ameliorated by the use of interval training.

Therefore, we believe that HIIT with the addition of HFNO might improve the exercise capacity in patients who suffer from ILD. This increment could justify its combined use and, thus, contribute to improve the effects of pulmonary rehabilitation programmes in these patients.

1.3 RESEARCH QUESTION

Will HIIT combined with HFNO lead to better outcomes (i.e. exercise capacity, QoL) in comparison to PR delivered without HFNO in ILD patients?

2 STUDY OBJECTIVES

2.1 PRIMARY OBJECTIVE

To evaluate the effects of an 8-week HIIT plus HFNO on exercise capacity of patients with ILD, in comparison to standard PR measured with a constant work rate cycle test (CWRCT) at 75% of the maximal workload obtained from a maximal CPET conducted beforehand. The high-intensity CWRET is considerably more responsive than incremental exercise tests or the 6-min walking test to assess the effects of interventions (18, 19, 20).

3 OUTCOME MEASURES

3.1 PRIMARY OUTCOME

The primary outcome will be Exercise Capacity, which will be assessed as endurance time (Tlim) during a constant work rate cycle test at 75% of the maximal workload (obtained beforehand from a maximal CPET).

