In addition, a Cardiopulmonary Exercise Test (CPET) will be carried out.

Furthermore, a Constant work rate Cycle Test at 75% of peak work rate (obtained from a maximal exercise test conducted beforehand) will be carried out. The participants will be able to rest for about 20 minutes between each test and we will offer them refreshments.

Physical activity levels in daily life will also be measured using Actigraph GT3x activity monitor, which will be delivered during the baseline appointment to use in their house for only 1 week before and 1 week after of the intervention, this is a belt that the participants will have to use like any other. After of the intervention they should return it to us during their post intervention appointment.

Moreover, two questionnaires called St George's Respiratory Questionnaire (SGRQ) and the Hospital Anxiety and Depression Scale (HADS), will have to be answered to measure the quality of life and anxiety and depression levels respectively. These test will be answered at home.

During the first day after of the intervention, participants will be undergone exactly to the same tests as in the baseline appointment, except height.

Intervention, a group of participants will be submitted to 8 weeks of a PR program based on HIIT plus HFNO and the other group will also be submitted to 8 weeks of a PR program based on HIIT but with conventional oxygen delivery without HFNO. Both HIIT will be performed at the same workload, which will be progressive throughout the 8 weeks and will be modified during each session. Starting with high load intervals at 60% of the maximal watts achieved beforehand during a maximal CPET divided by lower load intervals at 40% maximum load during the first week, and finishing with high load intervals at 110% maximum load separated by load intervals at 80% maximum load in the last weeks. Basically the participants will have to pedal in a stationary bicycle for 30 minutes (aerobic training), during the other 20 minutes the patients will do exercises for their upper limbs using Thera bands and dumbbells (strength training). Muscles of upper limbs to work will be deltoids, pectorals and biceps (3 series of 10 repetitions each). Finally the participants will receive 10 minutes of respiratory physiotherapy including techniques to eliminate phlegm, breathing exercises and ludic activities to train the respiratory muscles such as inflating balloons.

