4.7 BASELINE MEASUREMENTS

All the visits will take place in ward 204 (Respiratory Medicine) of the Royal Infirmary of Edinburgh (for participants from Scotland) and in the Royal Victoria Infirmary, Newcastle upon Tyne Hospital (for participants from Newcastle).

The visits during the first day before and after the intervention will take 2 hours each, and the following tests will be performed:

- Consent firstly will be re-confirmed at this visit.

- A blood test will be taken (6 ml) to know the levels of blood biomarkers associated with fibrosis that have been shown to be associated with disease progression (Inc. but not restricted to PAI-1, VEGF-A, PDGF-AA, PDGF-BB, Cystatin-C, Angiopotein-1, HE4/WFDC-2).
- A quadriceps maximal voluntary contraction test (QMVCT) will be taken to measure the strength of the quadriceps muscle.
- The shortness of breath will be assessed using the Modified version of the Medical Research Council scale (mMRC).
- Height.
- Weight.
- A Cardiopulmonary Exercise Test (CPET).
- A Constant work rate Cycle Test (CWRCT) at 75% of peak work rate (obtained from a maximal exercise test conducted beforehand) will be carried out.
- During this visit the PI will deliver to the participants the Actigraph GT3x activity monitor, which will have to be used at home for 1 week before and 1 week after of the intervention to measure the physical activity levels in daily life. The participants will have to return it during their post intervention appointment.
- Also during this visit two questionnaires called St George's Respiratory Questionnaire (SGRQ), which measure the quality of life will be delivered by the PI to be answered at home, the first one must be answered 1 day before of the intervention and returned during the first day of the intervention and the second one will have to be answered 1 day after of the intervention and returned during the post intervention appointment.
- Finally another 2 questionnaires called Hospital Anxiety and Depression Scale (HADS), which measure the anxiety and depression levels likewise will be delivered by the PI to be answered at home, the first one must be answered 1 day before of the intervention and returned during the first day of the intervention and the second one will have to be answered 1 day after of the intervention and returned during the post intervention appointment.

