6. STATISTICS AND SAMPLE SIZE

We did not calculate the sample size, because this is a Randomized, Controlled, Multicentre Proof-of-Concept (PoC) study. However, we expect to recruit 30 ILD patients approximately.

Categorical variables will be summarized by frequency. Continuous variables will be expressed as mean \pm standard deviation (SD) or mean (95% confidence interval [CI]). For comparisons with the data for categorical variables or continuous variables between groups, a chi-squared test or Student's t-test will be used. The statistical analysis will be conducted with the program SPSS version 23. The level of significance for all comparisons will be set at $p < 0.05$. We will collect any adverse event information and it will only be collected on an ae log.

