Appendix B

Constant Work Rate Exercise Test

Two operators will be present during the test. If the patient has cardiac issues or other clinical conditions which may be of concern then a doctor will be present. Before booking the appointment, ensure supervising doctor is available if appropriate.

Equipment Setup

Before patient testing, prepare the following;

- Mouthpiece for spirometry
- Serial sheet for spirometry
- CPET data sheet (located in the top drawer under the fridge)
- Mask (prepare a range of sizes)
- Flow head (located in plastic box on shelf on right of door)
- White ring adapter (located as above)
- ECG box (located as above)
- ECG electrodes (located in cupboard above the left of the sink)
- Skin prep pads (located as above)
- Ensure there is paper in the printer and the flap below is pulled out to catch it
- Ensure fan in room

- Print the patient referral (go to workbench on Trak, highlight patient + select print at the top of the page)
- Check if the patient has been before – if they have the patient should be tested at the same wattage

To Start System

Open gas cylinder and ensure adequate gas and pressure

Turn on system by pressing button on bottom right of the right hand monitor

Double click on “Breeze” icon on left hand screen to open program

Enter Login Name and Password and press “OK”

Ensure vacuum pump is on. If not, press “Vac” at the top of the screen (if the timer is stuck at 30:00, the vacuum pump is probably off)

Turn on the bike using the switch at the back below the seat

Calibration

Press “Calibrate” at the top of the screen

Take the 3L syringe from below the left hand side of the desk and attach the flow head to the blue rubber end with the side containing the holes facing into the syringe

Connect the umbilicus to the top of the flow head

Press “zero flow”

Press “start”

Withdraw and inject as directed until “calibration successful” is displayed

Replace the umbilicus to the port with the patterned side up

Remove the flow head and replace the syringe

Press the “O2 and CO2 analysers” tab

Click “calibrate” and wait until “calibration successful” is displayed

Click “OK” at the bottom left of the screen

Patient Details

For Existing Patients-

Click on yellow folder (Open Patient) to search for the patient.

Select Find.

Click on the drop down menu for search options, i.e. Name, ID etc.

Enter the search option selected to search for the patient.

If the patient is found it is highlighted.

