Stickers (called electrodes) and a band will be put onto the chest of the patients by themselves to monitor their heart rate and rhythm, therefore, their privacy will be ensured. Some men may need to have a small area of their chest shaved in order for the electrodes to stick to the skin. Seat patient on bike.

Check height of bike and adjust as necessary using the up and down arrows on the bike unit until the patient’s extended leg has a slight bend at the knee. The handlebars can also be adjusted by loosening the black handles on handlebar unit. (If the screen displays a menu, select PC Mode)

Attach ear probe for oximetry and run the cable over the hook on the back wall to ensure it stays out the way.

Fit the blood pressure cuff by feeling for the brachial pulse and fitting the orange tab over it, 2-3cm above the cubital fossa. Secure the cable through the Velcro on the handlebars.

Fit mask over the patient’s face. To ensure no leaks, instruct the patient to breathe in maximally then cover the hole in the mask with the palm of your hand as they exhale. Repeat with patient inhaling against the palm of your hand.

Establish appropriate workload for patient (at 75% of the maximal work load obtained from the maximal CPET conducted before).

Patient Testing

Click the “GX” tab at the bottom of the screen

Under “Script Name”, select “JAI”

Select the desired work rate increment by choosing the appropriate ramp under “default protocol”

Ensure that “Borg Scale” is selected to “6-20”

Click on “summary” to gain a value for VO₂ Max and write this on the CPET data sheet

Select the “test” tab at the bottom of the screen

Turn on SpO₂ monitor

Ensure the umbilical is connected to the black port located below the screen to the left and click “Gas AutoCal”.

Then plug the umbilical into the flow head and strap it over the patients head onto the headpiece

Click on the ECG icon on the right hand computer screen

Turn on the ECG box by pressing the button on the front of box

Observe the ECG

Press **Start**

Keep patient still on the bike

Take a resting BP measurement by pressing the red droplet with a circle inside

Record resting BP along with SpO₂ and HR on the CPET data sheet

Click on ECG event icon

Change Mason-Likar to “interpret all”

Monitor resting ECG for any abnormalities

Press **Exercise**

Instruct the patient to begin pedalling at 70 rpm

Take a baseline BP measurement by pressing the red droplet with a circle inside

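### The protocol does not say which CPET sets the load of the post-intervention constant work rate test, so the primary endpoint is not uniquely defined after training

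*Protocol*

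**What the plan says.** - **Protocol 3.1** gives the primary outcome as "endurance time (Tlim) during a constant work rate cycle test at 75% of the maximal workload (obtained beforehand from a maximal CPET"). Section 2.1 describes the load in the same terms.
- **Protocol 4.1** says that after the intervention "participants will be undergone exactly to the same tests as in the baseline appointment, except height". The schedule in 4.11 marks CPET and the constant work rate test at both appointments.
- **Protocol 4.7** uses one list for both visits: "The visits during the first day before and after the intervention will take 2 hours each, and the following tests will be performed". CPET comes first in that list, then the constant work rate test "at 75% of peak work rate (obtained from a maximal exercise test conducted beforehand) will be carried out".
- **Appendix B, Equipment Setup**, tells the operator to check whether the patient has attended before, and "if they have the patient should be tested at the same wattage".
- **Appendix B, Preparing the Patient**, then says "Establish appropriate workload for patient (at 75% of the maximal work load obtained from the maximal CPET conducted before", with no separate rule for a returning patient. The instruction for the end of the warm-up repeats this.
- **Appendix B, Patient Testing**, also contains "Select the desired work rate increment by choosing the appropriate ramp under" the default protocol, although the test is run at constant load.

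**The concern.** When the post-intervention test is set up, two maximal CPETs exist for each participant: one from before training and one from that visit. The load is tied to a maximal test done earlier, and both qualify.

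Endurance time is very sensitive to the load at which it is measured. At baseline watts, a patient whose peak has risen works at a smaller fraction of the new peak and should last longer. If the load is reset to 75% of the new peak, much of that improvement is absorbed by the harder test. The trial compares arms, so what matters is that the arm gaining more peak workload would be tested at the higher load.

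The two sites have different staff collecting data (4.12.2). They could apply different loads and both be following the protocol. A site-wide difference would mix two endpoints and add spread even where it did not favour an arm. No later analysis can repair this, because each participant performs the post-intervention test at one load only.

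**Working it through.** The protocol gives no effect size, SD or power, so there is no figure of its own to reproduce. The check is a reading of the text followed by two illustrations.

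**1. The text under each reading**
- *Baseline CPET sets the load.* Post-intervention load = 75% of baseline peak, the same watts as the baseline test. Sections 2.1, 3.1, 4.1 and 4.7 and both Appendix B instructions agree.
- *Same-day CPET sets the load.* Post-intervention load = 75% of the new peak. This follows the list order in 4.7. It is also how the words work at the baseline visit, where the earlier test is the CPET of that visit. It conflicts with the unchanged-watts line in Appendix B unless peak has not moved.

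**2. Load arithmetic** (assumed baseline peak 80 W)
- Baseline load = 0.75 × 80 = 60 W.
- Reset load = 0.75 × 80 × (1 + g), where g is the gain in peak.
- Baseline load as a share of the new peak = 75% / (1 + g).

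| Gain in peak | Baseline load | Reset load | Baseline load as % of new peak |
|---|---|---|---|
| 5% | 60 W | 63 W | 71.4% |
| 10% | 60 W | 66 W | 68.2% |
| 15% | 60 W | 69 W | 65.2% |
| 20% | 60 W | 72 W | 62.5% |

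The percentages do not depend on the assumed 80 W.

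**3. Effect on endurance time, between arms**

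Model: Tlim = W' / (load − CP), where CP is critical power and W' is the work available above it. Assumptions, none from the protocol: baseline Tlim 300 s; CP 50% or 60% of peak; peak and CP both rise 5% in the control arm and 10% in the HFNO arm; W' either fixed or rising with peak.

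Worked case, CP 60%, W' fixed:
- Baseline CP = 48 W and W' = (60 − 48) × 300 = 3600 J.
- Load kept at 60 W: control 3600 / (60 − 50.4) = 375 s; HFNO 3600 / (60 − 52.8) = 500 s; gap +125 s.
- Load reset: control 3600 / (63 − 50.4) = 286 s; HFNO 3600 / (66 − 52.8) = 273 s; gap −13 s.

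| CP | W' | Baseline watts: control, HFNO, gap | Reset load: control, HFNO, gap |
|---|---|---|---|
| 50% | fixed | 333, 375, +42 s | 286, 273, −13 s |
| 50% | rises with peak | 350, 413, +63 s | 300, 300, 0 s |
| 60% | fixed | 375, 500, +125 s | 286, 273, −13 s |
| 60% | rises with peak | 394, 550, +156 s | 300, 300, 0 s |

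CP at 65% is left out of the table. A 10% rise then puts CP at 71.5% of the old peak, close to the 75% load, and the model's times grow very large (857 s or more in the HFNO arm at baseline watts).

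**4. A case where a gain survives resetting.** If CP rises 10%, peak only 5% and W' is unchanged, then with CP at 60% Tlim at the reset load is 3600 / (63 − 52.8) = 353 s, which is 53 s above baseline.

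**5. Room for attenuation.** The protocol says "We did not calculate the sample size, because this is a Randomized, Controlled, Multicentre Proof-of-Concept (PoC) study" and expects about 30 patients. Assuming 15 per arm, a two-sided 0.05 level and a t-test, 80% power needs a standardised difference of about 1.06. A difference of 0.8 has 56% power; if it shrank to 0.5, power would be 26%.

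**The case against.** The best defence is that the protocol can be read consistently. Sections 4.1 and 4.10 use the same word, *beforehand*, for the CPET that sets the training load, and there it can only mean the baseline test. Every patient at the post-intervention visit is a returning patient, so the Appendix B line on unchanged watts applies to all of them. Section 2.1 chose this test for its responsiveness to interventions, which fits a fixed load.

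Much of this stands. A reader might infer that the protocol orders the load to be reset to the new peak; no section says so. It is also tempting to say that resetting would erase the training effect. The zero gap arises only when CP, W' and load are all scaled by the same factor, and step 4 of the working shows a gain that survives. The leftover ramp line is no evidence on this point either, since Appendix B elsewhere makes clear that the load is constant.

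The defence does not settle the matter. The consistent reading has to be assembled from several places, while the shared list in 4.7 puts a fresh CPET directly before the test it may set. The unchanged-watts line is a weak safeguard. The identical sentence is in the CPET procedure in Appendix A, where the test is a ramp, so it may be template text; that is inference. Appendix B then restates the 75% rule without reference to it.

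**Conclusion.** The concern holds as an ambiguity in how the primary endpoint is measured. The post-intervention load is not fixed to one value, and the instructions agree only if the baseline CPET is meant, which the protocol never states.

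If operators follow the order in 4.7 and use the same-day CPET, the part of the training gain that tracks peak workload is removed or masked. The between-arm difference is then biased toward zero and possibly reversed, provided one arm gains more peak than the other. Under the assumptions shown, a gap of 42 to 156 s becomes 0 or −13 s. The direction follows from the load arithmetic; the size rests on assumed gains, CP fractions and baseline time, and is not a prediction for this trial.

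This should be settled before the first post-intervention test. It is a bedside measurement rule, so a statistical analysis plan could not repair it afterwards.

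**What to change.** In 2.1, 3.1, 4.1, 4.7 and Appendix B, state: *The post-intervention constant work rate test is performed at the same absolute work rate in watts as the participant's baseline test, that is, 75% of the baseline CPET peak. The post-intervention CPET does not reset this load.*

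Two minor items of tidying in the same edit:
- Remove the ramp-selection line from Appendix B.
- State that Tlim starts when the 75% load is applied, after the 3-minute warm-up.

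The cost is wording in the protocol and the test procedure, plus informing operators at both sites. No visit, test or participant is added.
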